2.6 Correlative Studies Background

261 **Tumor pharmacodynamics (PD) evaluation:** Mutations in BRAF, specifically the BRAF V600E mutation, are the most commonly described mutations in DTC (7, 12, 32, 33). Preclinical models have confirmed that these mutations are oncogenic (10) and result in constitutive activation of the MAPK (RAS/RAF/MEK) pathway (34). Inhibition of BRAF and other signaling molecules in the MAPK pathway is thus conceptually appealing and early clinical trials evaluating BRAF inhibitors have been promising in patients with advanced thyroid cancer (35). Our primary hypothesis is that combination therapy with Dabrafenib (BRAFi) and Trametinib (MEKi) in patients with BRAF-mutant DTC will accentuate the vertical blockade of the MAPK pathway when compared to GSK2118438 alone, and that MAPK blockade will be associated with response to therapy. We propose using fine needle aspiration (FNA) tumor biopsies for PD monitoring. We have previously demonstrated in our study of sorafenib (a multikinase inhibitor with relatively weak BRAF inhibition) in papillary thyroid cancer that FNAs, obtained serially prior to and during treatment, can be used for PD monitoring of treatment with BRAF inhibitors (16). We performed immunohistochemistry (IHC) in biopsy specimens and tested for pERK, pAKT and pVEGFR. Monitoring of the same pharmacodynamics markers was also used with the potent and selective BRAF inhibitor PLX4032 in patients with metastatic melanoma (19). In the phase I PLX4032 trial, tumor biopsies obtained at baseline and day 15 was available for seven patients. Tumor levels of pERK, cyclin D1, and Ki-67 were markedly reduced at day 15 as compared with baseline in all specimens tested. These studies support the hypothesis that decreases in tumor pERK and Ki-67 will be seen with treatment, reflecting down regulation of MAPK. Increases in the levels of the sodium-iodine symporter (NIS) may also be seen, as BRAF activation suppresses NIS expression, leading to a loss of RAI sensitivity (36).

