9. CORRELATIVE STUDIES

9.1 Tumor pharmacodynamics (PD) evaluation (Tumor Biopsies pre-study and on-study)

9.1.1 Collection and Handling of Specimen(s): Fine needle aspiration (FNA) or core biopsy of tumor will be obtained at baseline and on C1D15 (+/- 5 days), for 7 patients in each arm of the study (14 patients total: "Biopsy cohort") who provide informed consent and have tumor lesions that are deemed by the study investigators to be accessible for biopsy. If funding permits, pre-study and on-study (C1D15) biopsies can be done in additional 6 patients on the trial. Optional biopsy/FNA will also be performed at progression in up to 5 patients in each arm of the FNA cohort who provide informed consent and who demonstrate initial radiographic response to therapy followed by radiographic progression. While these FNA/biopsies are invasive and will be done for research purpose, such procedures are routinely done for diagnostic purpose in clinical setting and are well tolerated in patients with thyroid cancer.

Biopsy/FNAs of accessible tumor will only be obtained under ultrasound or CT-guidance (unless palpable tumors) by medical personnel (e.g. cytologist, endocrinologist, surgeon, radiologist) with expertise in performing biopsy/FNA. Clinical trial research team member will be present bedside at time of biopsy to collect and process biopsy material. Detailed instructions describing this procedure will be included in a separate Study Lab Manual.

To assure that 10 evaluable paired FNA/biopsies are obtained from patients on each ARM of the study (total 20 patients), each participating center (total of 4 centers) will be required to enroll at least 5 patients who have paired biopsies. It is possible that 10 patients have pre-study biopsies but some of these patients might not be able to have 2nd on-study biopsy. Such case will be considered in-evaluable and additional patients will be recruited.

9.1.2 Shipping of Specimen(s): Frozen FNA samples will be batch shipped on dry ice to the Solid Tumor Translational Science (STTS) Resource at The Ohio State University Comprehensive Cancer Center along with the whole blood specimen and the frozen plasma samples collected for BRAF mutation testing. After the C2D1 collection time point. Shipping address and days of shipment details will be provided in the Lab Manual.

9.1.3 Site(s) Performing Correlative Study: Laboratory of [name] at Massachusetts General Hospital Cancer Center.

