9.1.4 Methods for Analysis of Tumor Pharmacodynamics studies: Prior to staining, tumor biopsy samples will be thawed and deposited onto at least 3 glass slides by centrifugation (Cytospin), and briefly dried. Slides can be stored at 4°C covered in PBS until staining. The samples will be stained with antibodies to anti-thyroglobulin antibodies (thyroid cancer cells), CD45 (white blood cells), panCytokeratins, DAPI (nuclei), and one PD biomarker (pERK, NIS, pAKT, p-p70S6K or Ki67), followed by appropriate secondary antibodies, utilizing immunofluorescence staining protocols developed by [name] in [name]'s laboratory at Massachusetts General Hospital Cancer Center. Additional proteins that provide information on tumor biology or pharmacodynamics may be tested as deemed appropriate by investigators. Immunofluorescence based cellular analysis has the primary advantages over traditional immunohistochemistry of: multiplexed analysis (e.g. simultaneous staining with three-four markers); sensitivity to scant samples; and the potential ability to quantify the results. Stained slides will be scanned within 48 hrs of staining on a Duet-3 automated scanning system (Bioview). Candidate tumor cells will be automatically scored according to pre-defined thresholds (e.g. CD45-negative, DAPI-positive, Cytokeratin-positive), and then visually inspected to confirm both cell morphology and specificity of staining. For pharmacodynamic analysis of the FNAs, the distribution of fluorescence intensities corresponding to pERK, pAKT, p-p70S6K, NIS and Ki67 will be determined and compared in pre- and on-treatment samples. The percentage change of tumor cell pERK, pAKT, p-p70S6K, NIS and Ki67 levels from pretreatment levels (both mean fluorescence intensity and number of pixels above predefined thresholds as assessed by antibody staining) will be calculated. When patient-derived samples are analyzed, control cell lines, to consist of cultured BRAF-mutant thyroid cancer cells untreated or treated with the same agents, will be analyzed simultaneously and in

parallel. Day to day variations in assay performance will be accounted for by comparing the data derived from such control samples.

9.2 BRAF mutation quantification in circulating plasma DNA (Peripheral Blood pre-study, on-study and at progression):

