- If the rates of the arms fall within $d = +/- 0.10$ of each other, the results of the study are considered statistically ambiguous and the regimens are considered similar with respect to their respective overall response rates. In this case, other factors are allowed to be taken into consideration when deciding on which regimen to bring forward into definitive Phase III testing. For this trial, we will specifically evaluate differences in the toxicity, PR+CR rate, progression-free survival, and correlative markers that indicate if the inhibitor therapeutic agents are hitting their respective targets.
- In the event that the success rates fall within .10 of each other, this study design assumes that there is a 50/50 chance of choosing the correct regimen. However, the choice of “d” used to determine whether or not other factors are considered is decidedly wide in order to allow the incorporation of the toxicity, translational, and other efficacy endpoints to be taken into consideration in this complex patient population. If one is clearly more promising than the other regimens and thus surpasses the other by the stated “d”, then it is less relevant to utilize other factors in this determination. The only potential exception is if the clearly most promising regimen has substantially more toxicity than the other regimen(s).

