In addition to the clinical outcomes of interest, we will also evaluate several correlative markers as well. Specifically, we will evaluate the serum thyroglobulin and assess how these levels correspond with achievement of response to treatment. We will assess this as between and across treatment arms; change in serum thyroglobulin levels will be evaluated between arms, and the impact of this change and how it is associated with response will be assessed using logistic regression analyses; we will look at how treatment arm and thyroglobulin levels are associated

with incidence of response. We will also evaluate differential levels using graphical methods (e.g. side-by-side boxplots) and two-sample t-tests (or nonparametric equivalent as necessary). We will also evaluate pharmacokinetic, pharmacogenetic, and pharmacodynamic markers. Differences in these markers and factors between patients who do vs. do not achieve response will be evaluated using chi-square statistics and two-sample t-tests depending on the type of marker/factor being compared based on clinical outcome group. Graphical analyses will also be used to assess potential trends and relationships between clinical response and these markers/factors.

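### Section 13.4 tests biopsy pharmacodynamic markers against response without regard to treatment arm, so the pooled comparison mixes the arm effect with any within-arm association

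*Combined protocol and SAP*

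**What the plan says.** Section 13.4 handles the correlative markers in one paragraph, in two ways.

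- **Thyroglobulin.** The arms are compared ("change in serum thyroglobulin levels will be evaluated between arms"), and arm enters the logistic regression for response ("we will look at how treatment arm and thyroglobulin levels are associated" with response).
- **Pharmacodynamic, pharmacokinetic and pharmacogenetic markers.** The stated method here is: "Differences in these markers and factors between patients who do vs. do not achieve response will be evaluated using chi-square statistics and two-sample t-tests". No arm term, stratification or within-arm analysis is given here or elsewhere.

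Section 2.6.1 states the primary hypothesis of the biopsy study in two parts: the combination "will accentuate the vertical blockade of the MAPK pathway when compared to GSK2118438 alone, and that MAPK blockade will be associated with response to therapy". The code is read here as dabrafenib, whose code elsewhere ends in 436. The first part compares arms; the second relates marker to response.

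Section 9.1.4 describes the laboratory analysis: marker intensities "will be determined and compared in pre- and on-treatment samples", with percentage change from the pretreatment level. It mentions no comparison of arms. Section 13.1.3 does list marker differences among the factors to be evaluated if the observed response rates lie within 0.10 of each other: "toxicity, PR+CR rate, progression-free survival, and correlative markers that indicate if the inhibitor therapeutic agents are hitting their respective targets". It names no marker, time point or method.

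Section 9.1.1 plans paired biopsies "for 7 patients in each arm of the study (14 patients total", and further down refers to 10 evaluable pairs per arm, 20 in total.

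**The concern.** If treatment arm shifts a marker and also shifts response, responders and non-responders differ in their mix of arms. A pooled two-sample comparison then shows a marker difference even where, inside each arm, the marker says nothing about who responds. The protocol predicts this configuration for the biopsy markers: deeper blockade on the combination (Section 2.6.1), greater efficacy on the combination (Section 2.5), and a design built on a 20-point difference in response (Section 13.1.3).

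At stake is the second part of the biopsy hypothesis. A pooled result could be read as showing that blockade is associated with response when it reflects only which regimen the patient received. The first part, the comparison of blockade between arms, has no stated analysis outside the conditional tie-break.

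**Working it through.** **Inputs from the plan.** Response rates 15% and 35%, 26 per arm, equal allocation, decision margin 0.10, ambiguous results counted as 50/50 (Section 13.1.3); 7 or 10 biopsy pairs per arm (Section 9.1.1). The 35% is assigned to Arm B, following the hypothesis in Section 2.5.

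**Assumptions not in the plan.** Two-sided alpha of 0.05; marker normal with SD 1, shifted by s SD in Arm B and independent of response within each arm; s from 0 to 3.

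**1. The plan's own figure.** Probability of correct selection = P(difference at least 0.10) + 0.5 × P(difference within 0.10), from exact binomials with 26 per arm. For 15% vs 35%: 0.8138 + 0.5 × 0.1805 = 0.904, against the stated 90%. For 10% vs 30% the result is 91.6% (stated: above 90%), and for 40% vs 60% it is 88.2% (stated: above 88%). The design rates are therefore used as they stand. The plan gives no power, alpha or sample-size rationale for the marker tests.

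**2. Mix of arms by response status.** With equal arms:

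- Arm B share of responders = 0.35 / (0.15 + 0.35) = 0.70
- Arm B share of non-responders = 0.65 / (0.85 + 0.65) = 0.433
- Difference = 0.267

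A shift of s SD in Arm B therefore produces an expected responder difference of about 0.27s SD with no within-arm association. At 40% vs 60% the shares are 0.60 and 0.40, giving 0.20s SD.

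**3. False-positive rate.** Simulation with 20,000 trials per scenario, dropping trials with fewer than 2 responders or fewer than 2 non-responders. The pooled t-test is compared with a linear model of marker on response and arm, at 15% vs 35%:

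| Patients per arm | Shift | Pooled t-test | With arm term |
|---|---|---|---|
| 7 | 1 SD | 6.4% | 5.0% |
| 7 | 2 SD | 9.1% | 5.2% |
| 7 | 3 SD | 10.9% | 5.1% |
| 10 | 1 SD | 7.2% | 5.2% |
| 10 | 2 SD | 11.1% | 5.2% |
| 10 | 3 SD | 13.2% | 5.0% |

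A separate run at 0.5 SD gave 5.4% (7 per arm) and 5.6% (10 per arm) for the pooled test. With equal response rates (35% in both arms) the pooled test stays near 5% at every shift, so the inflation needs arm to affect both marker and response.

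**4. How much data there is.** Expected responders in the biopsy cohort: 7 × 0.15 + 7 × 0.35 = 3.5, or 10 × 0.15 + 10 × 0.35 = 5.0. At 7 per arm, about 9% of simulated trials were dropped for too few responders.

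**5. Precision of a between-arm comparison.** For a 1 SD difference, a two-sample t-test has 41% power at 7 per arm and 56% at 10 per arm. Power of 80% needs a difference of 1.63 SD or 1.32 SD respectively.

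**The case against.** The strongest reply is that the problem is narrow, modest and exploratory. Much of that stands.

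- **Other markers.** A reader might infer that every marker-response test ignores arm. The thyroglobulin model names arm. Pharmacogenetic blood is drawn before the first dose (Section 9.6.1), so treatment cannot move it. Section 2.6.5 cites no interaction between the two agents, so there is little documented reason to expect dabrafenib exposure to differ by arm. Among patients as randomised, trametinib levels exist only in Arm B, so no arm term can be fitted.
- **Size.** A reader might infer that any marker moved by the combination will look like a predictor. At 7 to 10 per arm, a marker with no within-arm association is still non-significant in about 87-94% of trials (100% minus the rates in the table). Section 2.5 reports over 90% pERK inhibition in melanoma with each single agent, which may leave little room for a large difference between arms.
- **Larger figures.** With 26 per arm the same simulation gives 11.3%, 21.6% and 28.5%. Plasma BRAF is the candidate for that sample size, but Section 13.4 does not name it among these markers and Section 2.6.2 states no between-arm shift for it. Those figures should not be attached to the plan.
- **Tie-break.** A reader might infer that the bias feeds the Phase III choice. Markers enter that choice only when response rates are within 0.10, so arm and response are then nearly unrelated. With a marker measured in all 52 patients, the pooled test conditional on that event rejects 3.5%, 1.3% and 0.3% of the time at 1, 2 and 3 SD: conservative, not inflated.
- **Mediation.** Section 2.6.1 posits a chain from regimen to blockade to response. If it is true, the pooled association is partly real, and adjusting for arm removes the between-arm part. This argues against replacing the pooled analysis. It does not justify reporting it alone, because the pooled result cannot separate mediation from arm membership.
- **Between-arm comparison.** It is not wholly absent, since Section 13.1.3 plans to look at marker differences. That look is conditional and has no method, and the hypothesis in Section 2.6.1 is not conditional.

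**Conclusion.** The point holds for on-treatment biopsy pharmacodynamic markers. Their planned test against response ignores arm in a setting where the protocol itself expects arm to drive both variables. At the design rates the pooled responder difference carries a bias of about 0.27 SD for each SD of arm shift. The false-positive rate of a 5% test is about 6-11% at 7 per arm and 7-13% at 10 per arm for shifts of 1 to 3 SD, and near 5-6% at 0.5 SD. The shift sizes and the alpha are assumptions, and there is no bias if the response rates turn out equal. The primary endpoint and the main decision rule are unaffected. The unspecified between-arm pERK comparison is a secondary gap: Section 2.6.1 makes it the lead correlative question, and only a conditional tie-break touches it.

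**What to change.** In Section 13.4, for on-treatment pharmacodynamic markers and any other treatment-modifiable marker measured in both arms:

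1. Fit a linear model of the marker on response and arm. Report the arm-adjusted (within-arm) estimate with its confidence interval beside the unadjusted one. Base any statement that blockade is associated with response independently of regimen on the adjusted estimate.
2. Name one exploratory between-arm comparison, with a confidence interval, of the pERK change from baseline to C1D15, using the percentage-change measure of Section 9.1.4.
3. Reconcile the 7 and 10 pairs per arm in Section 9.1.1, since the precision of both analyses depends on that number.

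The cost is wording and one degree of freedom for the arm term; no new data are needed. Precision will remain low with 14 to 20 patients and 3.5 to 5 expected responders, and an arm term does not cure that, so both results should be labelled exploratory.

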13.1.2 Primary Endpoint

The primary endpoint for each of the treatment arms of this trial is overall objective response rate, defined as the proportion of patients who have a minor response (MR), partial response (PR), or complete response (CR) within the first 6 cycles of therapy. All randomized patients meeting the eligibility criteria who have signed a consent form and have begun treatment will be evaluable for response.

Complete response (CR) and partial response (PR) will be defined by RECIST 1.1, and minor response (MR) will be defined as 20-29% decrease in the sum of diameters of target lesions, taking as reference the baseline sum diameters. Any patients who have received at least one dose of treatment will be considered evaluable for these analyses. Patients will be analyzed in the treatment arm to which they were randomized. If a patient progresses, they will have met the primary endpoint classification for the purposes of this protocol (i.e. they will have had a response prior to progression or not). Patients' statuses prior to progression will be used in the assessment of response rates when evaluating the

primary endpoints for the treatment arms. Data on patients who cross over and receive treatment per another arm after progression will not be used in the decision analyses.

Rationale for using minor response as a part of objective response: Currently, many targeted therapy trials show clinically meaningful responses that are most evident only when reviewing waterfall plots that show % of tumor shrinkage in each patient. We have learned that PR and CR do not provide accurate assessment of clinical benefit. While stable disease is included as part of objective response in many solid tumors, it is not interpretable in patients with thyroid cancer due to overall slow-growing nature of cancer in many patients. Per RECIST 1.1, > 20% increase in tumor target lesions is considered significant and objective response in this case is defined as progressive disease. We therefore believe that 20-29% shrinkage of tumor represents true shrinkage that is clinically meaningful and is not by chance or measurement variation. Thus, we include MR as a part of objective response even though MR is not conventionally included.

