13.1.3 Statistical Design

To both evaluate whether or not each of these experimental treatment regimens are sufficiently active in this patient population as well as to screen these regimens for the most promising regimen to be carried forward to the phase III setting, this study utilizes a flexible screening design developed by Sargent and Goldberg (*Statistics in Medicine*, 2001). Overall, we have developed this study to be able to determine that one regimen is decidedly worth pursuing further over another if the true differential in the overall response rates between arms is 0.20. Overall, we have developed this study to be able to determine that one regimen is decidedly worth pursuing further over another if the true overall response rates are 15% versus 35%. This study design has 90% power to identify the correct regimen as most promising and thus the regimen to bring forward into larger and confirmatory studies. Based on these assumptions and constraints, 26 evaluable patients will be accrued to each arm to evaluate the regimens under the parameters specified. If our underlying assumptions regarding the true response rates associate with each of these arms is a little lower (e.g. 10% vs. 30%), we will have additional power for these analyses (i.e. >90%). Even if our true response rates corresponding to the treatment regimens being evaluated here are higher (e.g. 40% vs. 60%), we will still have sufficient power (>88%) to determine that one arm is more promising than another if it truly is with this number of patients per arm and the same rule for observed differential described below. The main decision rule is based on differential, and the above assumptions show a flexibility and sufficient power for identifying the most promising regimen even if our hypotheses regarding response rates are slightly off.

As part of this design, we define one treatment arm to be more promising than another if the actual observed overall response rate for each of the arms differ by 10% or more, in which case the regimen with the higher overall response rate will be recommended for further testing. If these rates differ by less than 10%, factors

other than the overall response rate will be considered.

- If one treatment arm has an overall response rate that is at least 0.10 higher than the other, then it will be deemed the most promising and carried forward to the phase III setting.

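### Section 13.4 formally tests every marker against yes/no response only; adding an arm-adjusted rank analysis of percent tumour change would recover much of the discarded information at almost no cost.

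*Combined protocol and SAP*

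**What the plan says.** Section 13.4 gives two formal routes from a marker to clinical outcome.

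- **PK, PGx and PD markers:** "Differences in these markers and factors between patients who do vs. do not achieve response will be evaluated using chi-square statistics and two-sample t-tests". Treatment arm is not mentioned in that sentence.
- **Thyroglobulin change:** "the impact of this change and how it is associated with response will be assessed using logistic regression analyses", with arm also considered.

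In both, the outcome is response yes or no. The only other provision linking markers to response is graphical and unspecified.

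Response is a cut of a continuous measure. Sections 11.1.4.1 and 13.1.2 count a fall of 20% or more in the sum of target diameters as at least a minor response. The sum is recorded at baseline (11.1.2) and disease is re-evaluated every 8 weeks (11.1). The PD markers are themselves percent changes (9.1.4).

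On cohort size, section 9.1.1 plans paired biopsies "for 7 patients in each arm of the study (14 patients total"), but later asks for 10 evaluable pairs per arm, 20 in total. PK covers the first 7 per arm in section 9.5.1 and the first 10 per arm in section 4.2. Pharmacogenetics and thyroglobulin cover all patients, up to 52.

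**The concern.** Reducing percent change to responder or non-responder treats 21% shrinkage like 80%, and 19% shrinkage like growth just short of progression. That costs power, and it matters most where patients are few. The planned response rates are low, so a cohort of 14 or 20 leaves a very small responder group.

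At stake are the pharmacodynamic hypothesis that MAPK blockade goes with response (2.6.1), the thyroglobulin objective and the PK/PGx/PD objective (1.2). The paired research biopsies are invasive, which is a reason to use their data fully. Nothing in the documents requires the cut for these exploratory analyses. Section 13.1.2 itself speaks of "clinically meaningful responses that are most evident only when reviewing waterfall plots that show % of tumor shrinkage in each patient".

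**Working it through.** **1. The plan's own figure.** Section 13.1.3 takes 26 per arm, "if the true overall response rates are 15% versus 35" percent, and an observed difference of at least 0.10 to select an arm, with a 50/50 choice otherwise. It states: "This study design has 90% power to identify the correct regimen as most promising". Exact binomial enumeration gives P(better arm ahead by 0.10 or more) = 0.8138 and P(ambiguous) = 0.1805. Correct selection is then 0.8138 + 0.5 × 0.1805 = 0.904, so the 90% reproduces. The 40% versus 60% scenario gives 0.7787 + 0.5 × 0.2058 = 0.882, matching the stated figure above 88%. The response-rate inputs can therefore be used as they stand. The documents give no power, effect size or significance level for the marker analyses.

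**2. Expected responders.**
- Biopsy, 14 patients: 7 × 0.15 + 7 × 0.35 = 3.5. The chance of fewer than 2 responders is 9%.
- Biopsy, 20 patients: 10 × 0.15 + 10 × 0.35 = 5. That chance is 2%.
- All 52 patients: 26 × 0.15 + 26 × 0.35 = 13.
- At 40% and 60%, 14 patients give 7 × 0.40 + 7 × 0.60 = 7.

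With 4 against 10, or 3 against 11, a two-sample t-test at two-sided 5% reaches 80% power only for a marker difference of about 1.8 or 2.0 SD.

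**3. Information kept by the cut.** For a normal outcome and a weak association, splitting at responder fraction p keeps φ(z_p)² / [p(1 − p)].
- p = 0.25: 0.3178² / (0.25 × 0.75) = 0.539, so 14 patients act like 14 × 0.539 = 7.5.
- p = 0.50: 0.3989² / 0.25 = 0.637.
- Other values: 0.43 at p = 0.15 and 0.60 at p = 0.35.

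**4. Power by simulation.** Marker and percent change are bivariate normal, arms respond at 15% and 35%, and the test level is two-sided 5% (assumed). The correlation r is also assumed. The rank method is a Spearman correlation adjusted for arm, except in the r = 0.3 row, which comes from an unadjusted Spearman at 25% response. A repeat run agreed with every row to within 3 percentage points, including r = 0.3 with arm adjustment.

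| Patients | r | Rank analysis of percent change | Responder t-test |
|---|---|---|---|
| 14 | 0.3 | 16% | 11% |
| 14 | 0.5 | 37% | 21% |
| 14 | 0.6 | 53% | 29% |
| 20 | 0.5 | 55% | 32% |
| 52 | 0.4 | 79% | 52% |

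At 40% and 60% response the gap narrows: 55% against 42% (14 patients, r = 0.6) and 80% against 62% (52 patients, r = 0.4). The t-test stands in for logistic regression in the thyroglobulin case.

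**5. Why arm must be in the model.** With 52 patients, no association within arm, rates of 15% and 35%, and an assumed 2 SD difference in the marker between arms, false-positive rates are 37% for a pooled Spearman, 22% for a pooled responder t-test and 5% for the arm-adjusted Spearman.

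**The case against.** **The planned tests answer the stated question.** Objective 1.2 relates thyroglobulin to response rate, and section 2.6.1 speaks of response to therapy. This stands. The responder comparisons should remain, and choosing them was not an error.

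**The waterfall remark opens an argument for the 20% cut.** The same paragraph of 13.1.2 concludes that 20–29% shrinkage is real rather than measurement variation, and regards stable disease as uninterpretable in this slow-growing cancer. So the section cannot be cited as preferring percent change for analysis. If movement below 20% is mostly noise, the gain is smaller than the simulation shows. Nor is there any stated reason to discard differences in depth among responders.

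**A reader might infer that the phase III choice is weakened**, because correlative markers are a tie-break factor when the arms differ by less than 0.10. Section 13.1.3 does not support that. It refers to markers showing whether the drugs hit their targets, which is target engagement and not the link between marker and response. Changing the outcome scale does not directly alter that input.

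**A reader might infer a loss of half in every case, from a cohort of 14.** The 14 is one of two stated biopsy sizes, and the loss falls to about 36% at 40% and 60% response.

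**Small numbers are the larger problem.** This also stands. At 14 patients and r = 0.3 neither method is informative. A rule for missing scans can cost power too: with 10% of patients given the worst rank for reasons unrelated to the marker, the gain fell to about 7–14 points at 15%/35% and 2–6 points at 40%/60%. It stayed positive in every case run.

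**Conclusion.** The point holds as an inexpensive improvement to secondary, exploratory analyses. Using yes/no response as the only formal outcome keeps about 54% of the information at the planned rates and about 64% at 40% and 60%. Both figures assume a roughly normal percent change and a weak association. At moderate correlations under the planned rates, the rank analysis adds about 16 to 27 percentage points of power (37 − 21 = 16; 79 − 52 = 27). At r = 0.3 with 14 patients it adds about 5. The correlations and the 5% level are assumptions, because the documents give neither.

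The addition does not make the biopsy or PK cohorts confirmatory. The documents also do not support reading this as a defect in the primary endpoint or the selection rule, both of which are untouched.

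**What to change.** In section 13.4:

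1. **Add** a pre-specified arm-adjusted rank analysis (partial Spearman, or rank regression with arm as a covariate) of best percent change in the sum of target diameters within 6 cycles on each continuous marker and on thyroglobulin change. For genotypes, add an arm-adjusted rank comparison of percent change across genotype groups.
2. **State the rule for patients without a usable value.** Give the worst rank to those whose first assessment is death or progression, including progression by a new lesion or in non-target disease. Report a sensitivity analysis for those with no scan for other reasons, such as toxicity or withdrawal.
3. **Keep** the chi-square, t-test and logistic comparisons by response alongside, since the objectives are worded that way.
4. **Reconcile** the biopsy size (14 or 20, section 9.1.1) and the PK size (7 or 10 per arm, sections 9.5.1 and 4.2), and describe results from these cohorts as exploratory.

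The cost is some wording and a few lines of code, because both measurements are already collected. The downside is one more set of exploratory tests and the need to defend a rank rule for missing scans.
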